STUDY PROTOCOL

NCT04606199

IRB ID: 19-27198

Examine the Effects of Meditation on Daily Psychological Stress Responses in Woman With a History of Child Adversity

Document date: November 4, 2021

Study design: The study uses a small micro-randomized trial design—a design that randomly assigns an intervention at each notification time point. In the proposed study, participants use the study app for 30 days and receive up to 3 notifications/day (morning, afternoon, evening). At each notification time point, participants first complete a brief ecological momentary assessment of their current psychological states (feeling stressed, positive/negative affect, stress appraisals, perseverative cognitions). Then, at each notification, each participant is randomized (50% probability) to either receive a brief mindfulness-based intervention (randomly selected from a pool of interventions) or no intervention. Thus, participants are randomized many times over the study (and each intervention is randomized many times to each person). Psychological states are again measured about 15 minutes after a notification to compare proximal (within 15 min) changes in intervention targets following an intervention vs. no intervention (proximal treatment effect).

Human Subjects Involvement, Characteristics, and Designs

I will recruit a new sample of adults, all of whom are women exposed to early life adversity. The rationale for my focus on this population is informed by the detrimental health effects of early life adversity, and by a lack of empirically-based non-pharmacological interventions to buffer or reverse risk pathways.

The study aims to develop an Ecological Momentary Mindfulness-based Intervention (EMMI) that targets maladaptive daily psychological stress responses. A micro-randomized trial will test target engagement and obtain qualitative acceptability/feasibility data during the development of the EMMI.

Inclusion criteria:

- 1) female
- 2) age 30-60
- 3) ≥2 Adverse Childhood Experiences
- 4) mild depressive symptoms (Patient Health Questionnaire ≥ 5)
- 5) having a smartphone

Exclusion criteria:

- 1) non-English speaker or unable to provide informed consent
- 2) current regular mindfulness practice (>20 min/week)
- 3) major psychiatric condition that necessitates priority treatment or interferes with participation, including psychoti disorder, bipolar disorder, Post-Traumatic Stress Disorder (PTSD), substance abuse/dependence, major depression (also indicated by PHQ-9 ≥ 15), self-harm or suicidal ideation (also indicated by PHQ-9, item 9)
- 4) Medication use and psychotherapy treatment has not been stable over the past 3 months.

Sources of Materials

The data collected in this study will include responses on self-report questionnaires, a short (15-20 minutes) diagnostic interview, app-based ecological momentary assessments and interventions, and audio-recordings of qualitative feedback on acceptability and feasibility. All data will be used for research purposes only. All data will be entered into or collected in electronic form. App-based ecological momentary assessment and intervention data will only use de-identified study ID numbers. Electronic data will be stored on a private, password-protected, encrypted hard drive accessible only to the PI or trained, authorized study staff. Hard copy data will be kept in locked filing cabinets in a locked office. Identifying information will be stored separately from data.

Potential Risks

Psychological distress from self-report questionnaires, diagnostic interviews, ecological momentary assessment of psychological responses, or generally heightened distress: Participants may experience temporary emotional discomfort or stress from responding to questions about their mental and physical health, early life adversities, and current psychological states. Although it is not anticipated that this study will cause significant psychological distress, it is likely that recruitment and assessment procedures will identify participants with elevated levels of distress. Protection against the risk that significant distress, and possibly worsening of depressive symptoms, and, in some cases, self-harm or suicidal ideation is developed during the study is outlined below.

Psychological distress from audio-recorded qualitative interview: Audio-recorded semi-structured interviews will obtain qualitative information on the acceptability and feasibility of the Ecological Momentary Mindfulness-based Intervention (e.g., satisfaction with each intervention component, preferred frequency/duration of assessment and intervention sessions, any challenges that participant encountered in using the app, and general feedback on app usability). Interviews carry a minimal risk for emotional discomfort and stress. Efforts will be taken to maintain the participant's comfort and study procedures will be stopped at the request of the participant.

Psychological distress from participation in the intervention: Participation in the Ecological Momentary Mindfulness-based Intervention (EMMI) includes short ecological momentary assessments (1-2 minutes/notification) and brief audio-guided mindfulness-based interventions. Previous studies of mindfulness interventions, including those recruiting individuals with early life adversity and trauma, demonstrated reduced distress (depression and anxiety), enhanced coping and mood, and improved quality of life. Thus, the EMMI carries minimal risk for emotional discomfort or stress.

Confidentiality: Participation in research may involve a loss of privacy, however information will be handled with the upmost confidentiality. One limit to confidentiality is if a participant is at imminent risk of harming herself (see more under Protection Against Risk).

Inconvenience: There may be some burden associated with filling out self-report questionnaires and completing repeated ecological momentary assessments and interventions in the flow of everyday life. However, participants will be provided with compensation for their time and effort.

ADEQUACY OF PROTECTION AGAINST RISKS

Recruitment and Informed Consent

Prior to study commencement, all procedures will be approved by the UCSF Committee on Human Research (CHR, the equivalent to IRB). Potential participants will be recruited using methods my mentors, advisors, and I have found successful in previous research with participants with high exposure to early life adversity.

Participants will be recruited via advertisements posted in Bay Area newspapers, listservs, Craigslist, Facebook, community-based self-help groups (e.g., Children of Alcoholics), and ResearchMatch. Research assistants will contact potential participants who respond to the recruitment ads by phone. Participants will undergo a phone screening to determine eligibility for the first assessment visit. If eligible for an initial visit, they will receive more details of the study by phone and a study appointment will be scheduled. At the beginning of the appointment, a trained research assistant will obtain written informed consent adhering to the following procedures: provide the potential participant with an opportunity to read the consent form; review the consent form in detail; answer questions; and, ask the potential participant to explain back in her own language what she understands the procedures to involve. Potential participants will have the opportunity to sign the form, decline participation, or to consider their decision further. The consent forms will provide the following information: background and purpose of the study, scope and length of participation, randomization procedure, study procedures, follow-up assessments, legal and ethical limits to confidentiality (including, for example, imminent risk of harming oneself), audio taping procedures, risks, benefits, alternatives, ability to discontinue participation, privacy and confidentiality, posting of clinical trial information at ClinicalTrials.gov, compensation, and whom to contact with questions. Participants will be assured that their decision to participate or decline participation in the study will have no effect on their current or future receipt of healthcare services at UCSF or affiliated clinics. Participants providing informed consent will complete further in-person screening procedures (e.g., complete PHQ-9) to determine eligibility. Only participants meeting all criteria (see above for inclusion and exclusion criteria) will be enrolled in the study.

Many efforts will be taken to promote retention: A research assistant will demonstrate the use of the app during the initial visit to ensure compliance. While using the study app, participants also have the option to postpone a notification if they are currently unavailable and prefer to complete assessments/interventions at a later time

point. Lastly, a trained research assistant will also make weekly phone contact with participants to address potential difficulties with adherence.

Protection Against Risk

Participants will be told that their participation is voluntary, and they can choose to withdraw from the study at any time without further obligation.

Psychological distress from self-report questionnaires, diagnostic interviews, and ecological momentary assessments: Participants will be told that they do not have to complete any questions, interviews, assessments, or interventions they do not want to complete and can stop at any time. Participants can also contact study staff to discuss any concerns.

Identification of participants with heightened distress: The proposed study aims to develop and pilot test an intervention tailored for individuals who have been exposed to early life adversity. As such, the recruitment and assessment procedures will identify individuals who will have subclinical or higher depressive symptoms. Some of these participants may be experiencing particularly significant distress and require clinical services beyond what the intervention will be able to provide. Thus, major psychiatric conditions (as determined by a diagnostic interview and the 9-item Patient Health Questionnaire, PHQ-9), including current moderately severe depressive symptoms (PHQ-9 ≥ 15) and self-harm or suicidal ideation (e.g., participant endorsed item 9 on PHQ-9: "Thoughts that you would be better off dead or of hurting yourself in some way") are an exclusion criterion. [name] study and mentoring team will immediately intervene and make appropriate referral for community care for participants. The study team will closely monitor depressive symptom severity and suicidal ideation among enrolled participants via weekly administration of the PHQ-9. Participants are instructed to make immediate contact with study personnel with any issues, questions, or concerns regarding worsening symptoms. At the first assessment visit, regardless of their current expressions of distress, participants are provided study contact information as well as local therapeutic and crisis resources. All study staff will be trained to probe for suicidal thoughts, intent, and psychotic behavior. If there is any suspicion of suicide risk or if participant endorses item 9 on the PHQ-9, study staff will immediately contact [name] so that appropriate steps can be taken to ensure the safety of the participants. [name] is a clinical psychologist who has extensive experience in assessing suicidal ideation and treating depression. She is a licensed Psychologist in the State of California. [name] and her study team will follow a written protocol for assessing and responding to suicide risk. This includes the evaluation of risk factors (e.g., plan, intent, access to lethal means) and protective factors (e.g., social support). For imminent risk, study staff will call emergency services and remain with the participant until emergency services arrive. For low to medium risk, study staff will provide mental health resources or psychological referrals, if needed.

Psychological distress from qualitative interviews (feedback on acceptability/feasibility): Participants will be invited to a private and comfortable interview room to provide feedback on the acceptability and feasibility of the study app. A research assistant will conduct the semi-structured interview with the participant. Participants will be asked to provide permission for the audio recording. For participants who do not provide permission, the research assistant will take written notes during the interview.

Discomfort associated with participation in the intervention: Participants will be provided with a thorough description of the Ecological Momentary Mindfulness-based Intervention prior to initiating treatment. They are notified that they can withdraw participation at any time without penalty. We expect that the proposed intervention would be associated with improved outcomes. However, important precautions will be taken to minimize risks, including weekly monitoring of depressive symptoms and suicidal ideation.

Confidentiality: All data will be handled with the maximal attention to participants' confidentiality. Subjects will be assigned unique, coded, confidential identifiers that will be used to label all data forms, data entries, and questionnaires. Identifiable information, such as name, will not appear on these materials or data files. The key linking the subjects' identity to their unique coded identifier will be kept in a confidential manner in a locked file cabinet within a locked office at UCSF or password protected on an encrypted and secure server at UCSF, which will only be able to be accessed by [name], and the study coordinator, when necessary. One limit to confidentiality is when a participant indicates being at imminent risk of harming herself. Participants will be informed of the legal and ethical limits to confidentiality during the consent process. If a participant endorses self-harm or suicidal ideation, we will follow above outlined procedures.

Inconvenience: All efforts will be made to minimize participant burden. Participants may be inconvenienced by the time spent during the daily ecological momentary assessments and interventions. Participants will be compensated for their time and effort.

POTENTIAL BENEFITS OF THE PROPOSED RESEARCH TO THE SUBJECTS AND OTHERS

There is strong conceptual basis to predict the benefit of a mindfulness-based ecological momentary intervention, including for participants with early life adversity. The minimal risks participants may experience in this study are reasonable in relation to anticipated benefits. Participants may experience improved psychological responding to daily stressors, improved mental and physical symptoms, as well as improved physiological markers as a result of daily mindfulness practices that are incorporated into everyday life. In the long-term, there are substantial benefits to be gained by developing and evaluating a mindfulness-based ecological momentary intervention to improve daily psychological stress responses, and ultimately to reduce or reverse psychological risk pathways associated with early life adversity.

IMPORTANCE OF THE KNOWLEDGE TO BE GAINED

Despite evidence that early life adversity can have detrimental consequences for midlife mental and physical health, there is a paucity of mechanism-focused non-pharmacological interventions. As a result of the proposed study, we will learn more about the psychological mechanisms linking early life adversity with midlife health outcomes, which will inform intervention targets, and about the acceptability, feasibility, and adherence of a mindfulness-based ecological intervention. This research will provide the preliminary data needed to evaluate the intervention in an adequately powered study.

STATISTICAL ANALYSIS

Using the centered and weighted least square method, which has been recommended for the analysis of proximal treatment effects in micro-randomized trials, I will test proximal (within 15 min) target engagement (also termed “proximal treatment effect”) by comparing changes (from current states at notification to about 15 min later) in each primary intervention target (positive/negative affect, threat/challenge appraisal, perseverative cognition) after an intervention vs. no intervention.

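### Does the felt-stress rating need a stated role in the analysis before this plan can stand?

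*Combined protocol and SAP*

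**What the plan says.** Under Study design, four constructs are rated at each of up to 3 notifications a day for 30 days: "current psychological states (feeling stressed, positive/negative affect, stress appraisals, perseverative cognitions". Each woman is then randomized with probability 50% to a brief intervention or to none. The same section adds: "Psychological states are again measured about 15 minutes after a notification to compare proximal (within 15 min) changes in intervention targets". The items of this second rating are not listed again.

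Under Human Subjects Involvement, Characteristics, and Designs, the purpose is given as: "The study aims to develop an Ecological Momentary Mindfulness-based Intervention (EMMI) that targets maladaptive daily psychological stress responses".

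The Statistical Analysis section is one sentence. It uses centered and weighted least squares to compare the change in "each primary intervention target (positive/negative affect, threat/challenge appraisal, perseverative cognition) after an intervention vs. no intervention". Felt stress is not named there or anywhere else as an outcome, covariate, moderator or condition for randomization. No moderator analysis of any kind is described.

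Under Importance of the Knowledge to Be Gained, the trial's place in the programme is stated: "This research will provide the preliminary data needed to evaluate the intervention in an adequately powered study".

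**The concern.** Felt stress heads the list of rated states and is the only one missing from the analysis sentence. The title and aim concern daily stress responses, and the section on potential benefits says: "Participants may experience improved psychological responding to daily stressors". A reader could reasonably expect to see whether an intervention lowers felt stress over the next quarter of an hour, and whether it works differently when a woman is stressed at the time of the prompt. Prompts are not tied to stress, so the data will mix stressed and calm moments, and the planned comparison averages over both.

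At stake would be two results useful to the later, larger study: the proximal effect on felt stress, and its modification by felt stress. If either is chosen only after the data are seen, it carries less weight than a prespecified result.

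**Working it through.** **Comparing the lists.** The plan gives no sample size, effect size, standard deviation or significance level, so there is no figure to reproduce.

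| Construct | Rated at the notification | Named in the analysis |
|---|---|---|
| Felt stress | yes | no |
| Affect, positive and negative | yes | yes |
| Stress appraisals (threat, challenge) | yes | yes |
| Perseverative cognition | yes | yes |

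Four constructs are rated and three are carried forward. The omission is real. It is not a contradiction, because Study design separates the states that are measured from the intervention targets whose change is compared, and it never calls felt stress a target.

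**What a moderator analysis would add.** From the documents: at most 30 × 3 = 90 decision points per participant, with 90 × 0.5 = 45 expected on intervention if all occur. Two quantities are not in the documents and are assumed: s, the share of prompts at stressed moments (25% or 50%), and r, the calm-moment effect as a fraction of the stressed-moment effect d (0 to 1). Take N independent prompts, residual standard deviation σ and 1:1 randomization.

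- Averaged effect: d[s + (1−s)r], with SE = σ√(4/N).
- Stressed-moment effect: d, with SE = σ√(4/(sN)). Ratio of its z to the averaged z: √s / [s + (1−s)r].
- Interaction: d(1−r), with SE = σ√(4/(N s(1−s))). Ratio of its z to the averaged z: (1−r)√(s(1−s)) / [s + (1−s)r].

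| r | Stressed-moment z ratio, s = 25% / 50% | Interaction z ratio, s = 25% / 50% |
|---|---|---|
| 0 | 2.0 / 1.4 | 1.7 / 1.0 |
| 0.25 | 1.14 / 1.13 | 0.74 / 0.60 |
| 0.5 | 0.80 / 0.94 | 0.35 / 0.33 |
| 1 | 0.50 / 0.71 | 0 / 0 |

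For example, at s = 25% and r = 0.25 the denominator is 0.25 + 0.75 × 0.25 = 0.4375. The ratios are 0.5/0.4375 = 1.14 and 0.75 × 0.433/0.4375 = 0.74.

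The stressed-moment z equals the averaged z at r = √s/(1+√s), which is 0.33 for s = 25% and 0.41 for s = 50%. Above that r the averaged effect has the larger z.

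The interaction SE relative to the averaged SE is 1/√(s(1−s)): 3.33, 2.50, 2.18 and 2.00 for s = 10%, 20%, 30% and 50%. It is never below 2.00.

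**Cost in tests.** Counting the slashed targets separately gives five. One new outcome plus five interactions is six tests. The chance of at least one false positive at 0.05, if independent and unadjusted, is 1 − 0.95⁶ = 0.265. These tests would be correlated, so this is only a guide.

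**What the raw rating would measure.** A moderator read at pooled low and high values mixes women who are generally stressed with moments that are unusually stressful. Assume an intraclass correlation of 0.3 for the rating. If the effect varied only with a woman's average stress, the pooled slope would still be 0.3 times the between-woman slope, and so would suggest momentary moderation where there is none. A sound version must separate the person mean from the deviation around it.

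**The case for a change.** The strongest case for a change is that it is cheap and apt. The rating precedes randomization, so it is a valid moderator. The change concerns analysis wording only. The study is developing an intervention for stress responses, so knowing when it works is directly useful, and prespecification costs little. Wide intervals are a reason to label the result exploratory, not to leave the item's role undefined. If the effect at calm moments were nil or reversed, the averaged effect would hide it; at r = 0 and s = 25% the stressed-moment z is twice the averaged z.

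Part of this stands. The plan commits to no use of felt stress, and a sentence saying what the item is for would be welcome. The rest is weaker. To say that the trial will not report felt stress goes beyond the text: the analysis sentence is confined to primary targets and excludes nothing. Adding felt stress as an outcome without new data assumes that it is rated again at 15 minutes, which is the natural reading but is not stated. The plan nowhere asks whether effects differ by momentary stress, and the passage on benefits is a human-subjects statement of what participants might gain, not an estimand.

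**Conclusion.** No change is needed. Followed as written, the plan yields valid averaged proximal effects on the targets it names, and these are stress responses in their own right. No stated number, rule or analysis is wrong or biased by the silence on felt stress. The outcome half of the concern is missing detail that analysts can fill sensibly, by reporting felt stress as a secondary proximal outcome if it was re-rated, or by using the pre-randomization rating as a control variable.

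The moderator half is an optional extra in a small, development-stage trial. Its gain is not assured: the interaction SE is at least 2.0 times the averaged SE, and the interaction z is at most 0.74 (s = 25%) or 0.60 (s = 50%) of the averaged z once r is between 0.25 and 1. It also needs more careful coding than the raw rating provides.

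These sizes rest on assumed s and r, a two-level split and independent prompts with constant variance. They do not cover opposite-direction effects (r below 0) or larger effects at calm moments (r above 1). The conclusion does not depend on them, since it follows from what the plan commits to. Should felt stress be used as a moderator later, it is best reported as exploratory estimates with intervals and without significance claims.

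### Does letting participants postpone a notification put the 15-minute follow-up ahead of the intervention it is meant to measure?

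*Combined protocol and SAP*

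**What the plan says.** The Study design section sets the order of events at a decision point. The pre-rating comes first: "At each notification time point, participants first complete a brief ecological momentary assessment of their current psychological states". Assignment follows: "each participant is randomized (50% probability" to a brief mindfulness exercise or to nothing. The outcome comes last: "Psychological states are again measured about 15 minutes after a notification". The Statistical Analysis section uses the same anchor and defines the change as running "from current states at notification to about 15 min later".

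The retention paragraph under Recruitment and Informed Consent adds that "participants also have the option to postpone a notification if they are currently unavailable and prefer to complete assessments/interventions at a later time"; the sentence ends with the word *point*. Under Potential Risks, the burden at each occasion is given as "short ecological momentary assessments (1-2 minutes/notification) and brief audio-guided mindfulness-based interventions", with no length in minutes for the intervention.

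The documents do not state a maximum delay, a rule for restarting the clock, an acceptable window for the follow-up, or how postponed occasions are analysed.

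**The concern.** Read separately, the two provisions seem to collide. The outcome is timed from the notification, while the participant may act on the notification later. If the clock stayed on the original notification, or if a woman could see her assignment and then put off only the exercise, the follow-up could arrive before or during the exercise. That occasion would count as an intervention occasion although no exposure had taken place, and the contrast would be pulled towards zero. Deferral of the exercise alone could occur only on occasions assigned to intervention, so the distortion would sit on one side of the comparison.

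The proximal contrast is the only analysis the plan describes, and the trial is meant to supply preliminary data for an adequately powered study. A diluted estimate could mislead the planning of that study.

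**Working it through.** The documents give no sample size, power, effect size or standard deviation, so there is no planned figure to reproduce. The check has two parts: which reading the text supports, and what the unfavourable reading would cost.

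**Which reading the text supports**

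1. *The whole notification moves.* The retention text makes the notification the object that is postponed, to a later time point. The Study design section attaches the pre-rating, the randomisation and the follow-up to the notification. A postponed notification therefore carries all three with it. Postponement comes before randomisation, so it cannot depend on the assignment. It changes which moments are sampled but does not bias the comparison at those moments. The share of occasions rated before exposure because of postponement is q = 0.
2. *The clock stays on the original notification.* With a delay above 15 minutes, the follow-up falls due before the pre-rating and the randomisation. The change defined in the Statistical Analysis section would then not exist. This reading makes the design unworkable.
3. *Only the exercise is deferred, after assignment.* The sole support is the slash joining assessments and interventions in the retention sentence. That phrase describes what is completed at the later time. Nowhere do the documents describe completing the pre-rating, learning the assignment and then deferring.

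**What the unfavourable readings would cost**

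Inputs from the documents:
- follow-up at about 15 minutes (Study design)
- assessment of 1 to 2 minutes (Potential Risks)
- "participants use the study app for 30 days and receive up to 3 notifications/day", so at most 30 × 3 = 90 occasions per woman, and at 50% probability about 90 × 0.5 = 45 interventions

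Assumed inputs: intervention length L, the share q of intervention occasions rated before any exposure, 80% power without dilution, and two-sided alpha of 0.05.

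With a fixed clock, the longest delay that still lets the exercise finish in time is 15 − assessment − L minutes:

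| Assumed L (min) | 1-min assessment | 2-min assessment |
|---|---|---|
| 3 | 15 − 1 − 3 = 11 | 15 − 2 − 3 = 10 |
| 5 | 15 − 1 − 5 = 9 | 15 − 2 − 5 = 8 |
| 10 | 15 − 1 − 10 = 4 | 15 − 2 − 10 = 3 |

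If a share q is rated unexposed, the effect retained is 1 − q and the data needed for equal power rise by 1/(1 − q)². Power is approximately Φ[(1 − q)(1.96 + 0.84) − 1.96].

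| Assumed q | Effect retained | Data needed | Power |
|---|---|---|---|
| 0 | 100% | × 1.00 | 80% |
| 5% | 95% | × 1.11 | 76% |
| 10% | 90% | × 1.23 | 71% |
| 20% | 80% | × 1.56 | 61% |
| 30% | 70% | × 2.04 | 50% |
| 50% | 50% | × 4.00 | 29% |

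The arithmetic is sound, but every row below q = 0 needs reading 2 or reading 3, and the documents support neither. For delays over 15 minutes, reading 2 would not even produce this smooth dilution, because the change score would be undefined.

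**Does the interval differ between conditions?** If the follow-up is fixed and only the exercise is deferred, the scheduled interval from pre-rating to follow-up is the same in both conditions. If the whole notification is deferred before randomisation, any variation in the interval is balanced by the randomisation. Neither case gives a scheduled interval that differs by condition.

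**The case for a change.** The best case for a change is that the event starting the 15 minutes is part of the outcome definition, and a reader should not have to infer it. The favourable reading is plausible but unwritten. Two sentences and an app setting would settle it: time the follow-up from submission of the pre-rating in both conditions, and allow postponement only before that rating is opened. For so little effort, even a modest risk might justify acting.

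Part of this stands. The text is silent on restarting the clock, on the window and on late occasions, and a sentence on each would make it easier to read.

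The rest does not carry. Timing from the pre-rating is close to what is already planned, since the change runs from the states reported at the notification and the same timing applies in both conditions. Nor would the setting remove the feared problem: a woman who starts the audio late would still be rated before finishing it. Such an occasion is non-adherence. An analysis by assignment includes it and estimates the effect of being assigned the exercise, which is a legitimate target.

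**Conclusion.** The concern does not call for a change. The real gap is one of wording: nothing says outright that a postponed notification takes its pre-rating, randomisation and follow-up with it. The order of events in the Study design section already implies this, and under that reading the dilution from postponement is zero.

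The documents do not show that follow-ups precede the intervention, that any distortion would fall on one condition, or how large it would be. The losses of 10% to 30% and the inflation factors of 1.23 to 2.04 rest on assumed shares and apply to no stated power target. The study calls itself small and preliminary.

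This conclusion assumes that the app treats a postponed notification as a new decision point. If it instead let women defer the exercise alone after seeing their assignment, the dilution formula would apply, with q taken from the app's records where these show completion times.
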